**1. Recruitment Details:**

Recruitment period: between October 2009 and December 2010

Type of location: All of the documents were obtained from the Diabetic Foot Centre (DFC) in Wroclaw, Poland, where the patients had consultations, covered a period of fifteen months of work.

**Pre-assignment Details:**

Patients without previous ulcerations or foot surgery were evaluated- if there were any doubts, the patient's results were not taken into consideration.

**Arm/Group Information:**

**Arm/Group Title:**

Non-ulcer patients with diabetes mellitus.

**Arm/Group Description:**

Patients with diabetes mellitus but without active or past foot ulcer or surgical procedure within the feet.

**Type of Units Assigned:**

Not applicable

**Period(s):**

All medical records were analyzed between September 2012 and January 2014.

**Started:**

974 medical records

**Completed:**

974 medical records

**2. Baseline Characteristics:**

**Arm/Group Information**

Table 1. Baseline characteristics of the study population: sex, age, BMI

NT	Age (years) mean $\pm$ SD (range)	BMI (kg/m  ) mean $\pm$ SD (range)
974	64.6 $\pm$ 11.15 (21-90)	29.9 $\pm$ 5.22 (18.5-66.7)
451♂	63.8 $\pm$ 10.9 (24-90)	29.44 $\pm$ 4.74 (18.5-46.2)
523♀	65.3 $\pm$ 11.33 (21-88)	30.4 $\pm$ 5.56 (19-66.7)

NT- total number of patients    SD-standard deviation

**Baseline Measure Information**

**Baseline Measure Title**

- **Age:**

**Age, Continuous:** mean with SD (Table 1)

**Age, Categorical:** \* $\leq$ 40 years

\* 41-50 years

\* 51-60 years

\* 61-70 years

\* 71-80 years

\* 81-90 years

- **Sex:** Female (♀), Male (♂) (Table 1)
- **BMI :** mean with SD (Table 1)

### **Baseline Measure Description**

**Age-** was calculated based on patients ID (identification) number (in Poland each ID number contains date of birth).

**Sex:** based on information from medical records

**BMI:** BMI was calculated based on the height and weight assessed during the visit and recorded in the medical records. BMI was defined as the body mass in kilograms divided by the square of the body height in meters, and expressed in units of  $\text{kg}/\text{m}^2$

### **Measure Type**

- Count of participants
- Mean

## **Measure Dispersion**

- Standard Deviation
- range

## **Number of Baseline Participants**

974 participants: women: 523, men: 451;

Age categories: ≤40: 36;

41-50: 51;

51-60: 233;

61-70: 333;

71-80: 269;

81-90: 52

### **3. Outcome Measures**

#### **Primary Outcome Measure**

**Outcome Measure Title:** Abnormal Plantar Pressure Distribution (APD)

**Outcome Measure Description:** APDs were analysed for the forefoot (P1- 25% of the foot length) and mid-foot (P3- 28% of the foot length), with a separate evaluation for the lateral (P2) part of the mid-foot (the edge of the foot). The load of the hallux (20% of foot length) and rearfoot (27% of the foot length) was not analysed. The mentioned percentage for the appropriate lengths from the foot

print was calculated from the total length measured from the heel end to the furthest point (1st toe or other toe). We used colour intensity analysis to demonstrate the presence of the maximum pressure (peak pressure) represented by the hottest colour – the red one. If necessary, the patient repeated the test until a correct impression of the foot (symmetric with the corresponding location of the centre of the mass). For the heel the red colour does not constitute pathology, because this colour always indicates a site of greatest pressure (typically presented within the heel). The heel load evaluation is therefore only useful if it includes absolute pressure value assessment.

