#### **Arm/Group Description:**

1. Patients with no APD- participants with correct load rates based on the print (three main load points on the both feet: central part of the heel; the 1st and 4th - 5th metatarsal heads)
2. Patients with APD- participants with at least one abnormal load point, within forefoot and/or mid-foot and/or lateral edge of the foot, on at least one foot

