**Outcome Measure Data Table**

**Primary Outcome Measure: Outcome Measure Title: Abnormal Plantar Pressure Distribution (APD): Outcome Measure Data Table**

**Measure Type:** count of participants

Table 1 APD in: forefoot, lateral part of the foot, mid-foot.

NT	Patients with at least one APD regardless of the location	APD within forefoot	APD within lateral part of the foot	APD within mid-foot
♂ n=451	408	380	78	5
♀ n=523	486	426	138	21
974	894	806	216	26

NT- total number of patients

APD- abnormal plantar pressure distribution

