**Secondary Outcome Measure: Outcome Measure Title: BMI. Outcome Measure Data Table**

**Measure Type:** count of participants

Table 3. BMI <35 and BMI ≥35 in patients with and without APD within: forefoot, lateral part of the foot, mid-foot.

NT	Patients without APD within the forefoot	Patients with APD within the forefoot	Patients without APD within lateral part of the foot	Patients with APD within lateral part of the foot	Patients without APD within the mid-foot	Patients with APD within the mid-foot
BMI						
<35	128	693	665	156	808	13
821						
BMI						
≥35	40	113	93	60	140	13
153						

BMI- body mass index; NT- total number of patients

APD- abnormal plantar pressure distribution

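### Does the mid-foot column need correcting because the lateral zone is worded as part of the mid-foot?

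*Combined protocol and SAP*

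**What the plan says.** Section 3, Primary Outcome Measure, divides the footprint by length. The forefoot is P1 at 25%, the middle band is "mid-foot (P3- 28% of the foot length", and the text adds "with a separate evaluation for the lateral (P2) part of the mid-foot (the edge of the foot". The two end bands are set aside: "The load of the hallux (20% of foot length) and rearfoot (27% of the foot length) was not analysed".

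The Arm/Group Description for the primary outcome classes a patient as having APD if there is an abnormal load point "within forefoot and/or mid-foot and/or lateral edge of the foot, on at least one foot".

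The APD data table is titled "APD in: forefoot, lateral part of the foot, mid-foot". Its total row, "974 894 806 216 26", gives patients, any APD, forefoot, lateral and mid-foot in that order. Table 3 splits each location by BMI. Under "Patients without APD within the mid-foot" it shows 808 patients with BMI below 35 and 140 with BMI of 35 or more.

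No passage states the border between P2 and P3, or whether one patient can count in both.

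**The concern.** Read literally, the outcome description makes P2 a piece of the mid-foot. The length bands use up the whole foot without giving P2 a band of its own, and no width is given for it. A reader who carries that wording to the tables would expect any patient with lateral APD to be a mid-foot case too. The tables do not behave that way: about a fifth of the patients shown as free of mid-foot APD have lateral APD. P2 is also named differently in the tables than in the description, and the tables carry no P-codes.

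What would be at stake is the reading of one location. Someone who took 26/974 = 2.7% as the prevalence of APD anywhere across the mid-foot would understate it considerably. They might also treat the 948 as a clean comparison group in the BMI analysis.

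**Working it through.** **Inputs.** Length bands from the Primary Outcome Measure description; totals and sex rows from the APD data table; BMI rows from Table 3.

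**1. Length bands.** Hallux 20 + forefoot 25 + mid-foot 28 + rearfoot 27 = 100%. P2 therefore has no length of its own and has to lie across the width of a band.

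**2. Reproducing the tabulated totals.**
- Mid-foot APD: 13 + 13 = 26 by BMI; 5 + 21 = 26 by sex.
- Lateral APD: 156 + 60 = 216 by BMI; 78 + 138 = 216 by sex.
- No mid-foot APD: 808 + 140 = 948 = 974 - 26.
- Table 3 rows: 808 + 13 = 665 + 156 = 821; 140 + 13 = 93 + 60 = 153.

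All agree.

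**3. Lateral APD inside the column for no mid-foot APD.** The minimum is n(P2) - n(P3), reached if every mid-foot case is also a lateral case. The maximum is n(P2), reached if none is.

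| Group | Minimum | Maximum | Column total | Share |
|---|---|---|---|---|
| All | 216 - 26 = 190 | 216 | 948 | 20.0% to 22.8% |
| BMI 35 or more | 60 - 13 = 47 | 60 | 140 | 33.6% to 42.9% |
| BMI below 35 | 156 - 13 = 143 | 156 | 808 | 17.7% to 19.3% |

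Both stratifications return the same minimum: 47 + 143 = 190 by BMI, and (78 - 5) + (138 - 21) = 73 + 117 = 190 by sex.

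**4. Testing the two readings.** If the mid-foot count included P2, it would have to be at least 216. It is 26, so that reading fails. If the zones were counted separately, the location counts need only cover the patients with APD outside the forefoot alone:
- All: 894 - 806 = 88, within 216 + 26 = 242.
- Men: 408 - 380 = 28, within 78 + 5 = 83.
- Women: 486 - 426 = 60, within 138 + 21 = 159.

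This reading is coherent throughout. The sum 806 + 216 + 26 = 1048 exceeds 894, so some patients appear in more than one location.

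**5. Dependence of the primary outcome on the border.** APD is defined as an abnormal point in any of the three zones. Moving a red area from P2 to P3, or the reverse, leaves the patient in the APD group. The split of 894 with and 80 without is unaffected.

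**6. BMI comparison.** The higher share of lateral APD in the high-BMI part of the column is already visible in the neighbouring Table 3 columns: 60/153 = 39.2% against 156/821 = 19.0%. It adds no new imbalance and does not alter the test of the mid-foot column, which compares 13/153 = 8.5% with 13/821 = 1.6%.

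**The case for a change.** The strongest case for a change is that an outcome definition should not have to be deduced from its results. A separate evaluation could mean a sub-analysis nested in the mid-foot, and a list joined by and/or does not make its members exclusive. The reader has to notice that 216 exceeds 26 to rule nesting out. If all 216 lateral cases lie where the description puts P2, APD anywhere across the mid-foot affects 216 to 242 of 974 patients (22.2% to 24.8%) against the tabulated 2.7%. That gap would matter to anyone comparing mid-foot results between studies, and a clarifying sentence costs almost nothing.

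Part of this stands. The rule separating P2 from P3 is unwritten, and so is any overlap between them (0 to 26 patients). The misreading is unlikely to last, though, because the two figures sit side by side in the APD table. The combined P2-or-P3 quantity is not an outcome that the document defines or reports.

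The obvious relabelling, a mid-foot column that excludes the lateral edge, would also claim more than the document shows. The separation could be anatomical, or it could be a coding rule under which a print confined to the edge is coded P2 only. In the second case P3 might span the full width, and the new label would be wrong.

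**Conclusion.** No change follows. The wording is loose, and the figures behind the concern are exact: 948 patients in the column, of whom 190 to 216 have lateral APD. Calling this lateral mid-foot APD assumes that all 216 lie where the outcome description places P2.

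The separate code, the separate evaluation, the separate listing in the group definition and the adjacent columns all point to separate counting. The counts then exclude the alternative. Writing the P2/P3 rule down would help a careful reader, but it is missing detail that the tables already let the reader supply. It would change no count, no chi-square test on the tabulated columns, and neither side of the 894/80 split.

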### **Outcome Measure Time Frame**

The APD rating for each patient was one-off and took place during one visit in the Centre. Data for all participants come from 15 months of observation.

### **Arm/Group Information**

#### **Arm/Group Title:**

1. Patients with no APD.
2. Patients with APD.

#### **Arm/Group Description:**

1. Patients with no APD- participants with correct load rates based on the print (three main load points on the both feet: central part of the heel; the 1st and 4th - 5th metatarsal heads)
2. Patients with APD- participants with at least one abnormal load point, within forefoot and/or mid-foot and/or lateral edge of the foot, on at least one foot

### **Secondary Outcome Measure**

**Outcome Measure Title:** Neuropathy

**Outcome Measure Description:** Parameters for symmetric, peripheral, sensory-motor neuropathy was assessed. The motor component of the neuropathy causes muscle atrophy within the feet with subsequent abnormal distribution of the plantar pressure (invisible in standard physical examination) then visible feet deformity and calluses. Information about visible deformities and calluses were derived from physical examination. Deformities included hammer- or claw-toes, hallux valgus, visible flat feet, or “other visible deformities “. The calluses were defined as thick, hardened layers of the skin. The sensory component of the neuropathy was assessed with a questions and clinical evaluation. A skilled nurse asked patients about stinging, numbness, tingling, or burning of the foot for the questionnaire items. Ten-gram monofilament and tuning fork (128 MHz) tests were administered. Monofilament was applied in 10 locations on the sole (calluses were avoided) and one on the dorsal part of the foot for checking the loss of protective sensation. A positive monofilament test was considered to be the lack of sensation of tightness in at least 6 of 11 tested sites. The tuning fork was applied for vibration detection to both ankles, the first metatarsophalangeal joint, and the anterior aspect of the shin bone sites. A positive vibration test was considered to be no detection of vibration in three of four test sites.

The condition required for the occurrence of these disorders (MN-motor and/or PSSN- peripheral, symmetric, sensory neuropathy) was symmetry.

### **Outcome Measure Time Frame**

The neuropathy assessment for each patient was one-off and took place during one visit in the Centre. Data for all participants come from 15 months of observation.

### **Arm/Group Information**

**Arm/Group Title:**

1. PSSN negative
2. PSSN positive
3. MN negative
4. MN positive

**Arm/Group Description:**

1. Patients without sensory component of the neuropathy- participants with asymmetrical disturbances and/or less than two positive test results and without minimum one typical neuropathy symptom as well as patients with less than two positive test results and with typical neuropathy symptom.
2. Patients with sensory component of the neuropathy- participants with two positive test results and typical symptoms of the neuropathy or participants with two positive test results without typical neuropathy symptom. The condition required for the occurrence of these disorders was symmetry.
3. Patients without motor component of the neuropathy- participants without visible feet deformity and/or calluses.
4. Patients with motor component of the neuropathy- participants with visible feet deformity and/or calluses. The condition required for the occurrence of these disorders was symmetry.

**Outcome Measure Title:** Body Mass Index

**Outcome Measure Description:** BMI was defined as the body mass in kilograms divided by the square of the body height in meters, and expressed in units of  $\text{kg}/\text{m}^2$

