**Secondary Outcome Measure: Outcome Measure Title:** Neuropathy; **Overall Number of**

**Participants Analyzed:** 974; 1. PSSN negative: 907 2. PSSN positive: 67

3. MN negative: calluses: 645; foot deformity: 798

4. MN positive: calluses: 329; foot deformity: 176

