**Secondary Outcome Measure: Outcome Measure Title: Neuropathy: PSSN and MN Outcome Measure Data Table**

**Measure Type:** count of participants

Table 2. PSSN and MN (calluses and visible foot deformities) in patients with and without APD.

NT	Patients with Abnormal Plantar pressure Distribution	Patients without Abnormal Plantar pressure Distribution	NT
Patients without Peripheral Symmetric Sensory Neuropathy	833	74	907
Patients with Peripheral Symmetric Sensory Neuropathy	61	6	67
Patients without Calluses	588	57	645
Patients with Calluses	306	23	329
Patients without Foot Deformity	728	70	798
Patients with Foot Deformity	166	10	176

NT- total number of patients

APD- abnormal plantar pressure distribution

PSSN- peripheral, symmetric, sensory foot neuropathy

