### Statistical Analyses

#### Statistical Analysis Overview

The Statistica 9 PL (StatSoft) software package was used for statistical analysis.

The Kolmogorowa - Smirnowa test was used in the distribution analysis.

According to the result of the analysis the parametric, T-test or nonparametric, U Mann-Whitney test was used in further calculations.

The Chi-square test was used to determine the association between two categorical variables.

A *P* value <0.05 was considered statistically significant.

Data are presented as means ( $\pm$ S.D.).

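### Motor neuropathy is defined as one composite outcome, but only its two component signs are counted and tabulated against APD

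*Combined protocol and SAP*

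**What the plan says.** Under the secondary outcome Neuropathy, the Arm/Group Title list has a single MN-negative and a single MN-positive group. The Arm/Group Description defines them as follows:

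- Positive: "Patients with motor component of the neuropathy- participants with visible feet deformity and/or calluses".
- Negative: "Patients without motor component of the neuropathy- participants without visible feet deformity and/or calluses".

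The Outcome Measure Description takes both signs from the clinical examination ("Information about visible deformities and calluses were derived from physical examination") and adds a condition: "The condition required for the occurrence of these disorders (MN-motor and/or PSSN- peripheral, symmetric, sensory neuropathy) was symmetry".

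The Analysis Population Information enters two figures under each label: "MN negative: calluses: 645; foot deformity: 798" and "MN positive: calluses: 329; foot deformity: 176". Table 2 is titled "PSSN and MN (calluses and visible foot deformities) in patients with and without APD". It has one pair of rows for calluses and one for foot deformity, each split by APD, and no row for MN itself.

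The Statistical Analysis Overview gives a general rule, with a 0.05 threshold: "The Chi-square test was used to determine the association between two categorical variables".

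**The concern.** A patient is MN positive with either sign, so MN is a union of two signs, and its size depends on how many patients have both. That overlap is not reported. The two count pairs cannot both be the MN groups, and possibly neither is.

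Two points of wording leave the groups more open still:

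- The negative definition repeats the and/or of the positive one. It can mean lacking both signs, which is the complement of MN positive, or lacking at least one of them, which is not.
- Neither the population counts nor Table 2 says whether 329 and 176 are limited to symmetric signs.

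The motor component is one of the two parts of the neuropathy outcome, and the document's own rationale presents it as a cause of abnormal pressure distribution. The sensory part (PSSN), also built from several elements, is reported as one classification (907 negative, 67 positive) with one 2x2 table against APD. The motor part has no such result. Neither the prevalence of MN nor its association with APD can be read from what is printed. The APD, PSSN and BMI counts are not affected.

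**Working it through.** **Inputs (Table 2 and Analysis Population Information)**

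| | APD | No APD | Total |
|---|---|---|---|
| Calluses | 306 | 23 | 329 |
| No calluses | 588 | 57 | 645 |
| Deformity | 166 | 10 | 176 |
| No deformity | 728 | 70 | 798 |
| All | 894 | 80 | 974 |

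**1. The printed counts reproduce.** 329 + 645 = 974 and 176 + 798 = 974. In the APD column, 306 + 588 = 894 and 166 + 728 = 894. Without APD, 23 + 57 = 80 and 10 + 70 = 80. There is no arithmetic error, and the table is intact.

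**2. Each sign against APD** (uncorrected chi-square, Wald 95% CI; the documents print no such tests).

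- Calluses: OR = (306 × 57)/(23 × 588) = 1.29 (0.78 to 2.13), p = 0.32.
- Deformity: OR = (166 × 70)/(10 × 728) = 1.60 (0.81 to 3.16), p = 0.18.

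**3. Size of the composite.** Assume that the counts cover symmetric signs only and that MN negative is the complement of MN positive. With b patients having both signs (0 to 176), MN positive = 329 + 176 − b = 505 − b.

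- MN positive: 329 to 505 of 974 (33.8% to 51.8%).
- MN negative: 974 − 505 = 469 to 974 − 329 = 645 (48.2% to 66.2%).

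So 176/798 cannot be the MN groups. At least 329 − 176 = 153 of the 798 deformity-free patients have calluses and are MN positive by definition. The pair 329/645 is right only if every patient with a deformity also has calluses.

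**4. The other reading of MN negative.** If it means lacking at least one sign, it numbers 974 − b, or 798 to 974, so 645 cannot be that group. Patients with exactly one sign number 505 − 2b, or 153 to 505, and would fall in both groups.

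**5. Composite against APD.** Let x be the deformity patients with APD who also have calluses (0 to 166), and y the same without APD (0 to 10). MN positive is then 306 + 166 − x = 472 − x of 894 with APD, and 23 + 10 − y = 33 − y of 80 without.

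| x | y | MN+ with APD | MN+ without APD | OR (95% CI) | p | Yates p |
|---|---|---|---|---|---|---|
| 166 | 0 | 306 | 33 | 0.74 (0.47 to 1.18) | 0.21 | 0.25 |
| 166 | 10 | 306 | 23 | 1.29 (0.78 to 2.13) | 0.32 | 0.38 |
| 83 | 5 | 389 | 28 | 1.43 (0.89 to 2.31) | 0.14 | 0.175 |
| 57 | 3 | 415 | 30 | 1.44 (0.90 to 2.31) | 0.125 | 0.156 |
| 0 | 0 | 472 | 33 | 1.59 (1.00 to 2.53) | 0.048 | 0.062 |
| 83 | 8 | 389 | 25 | 1.69 (1.04 to 2.77) | 0.034 | 0.045 |
| 0 | 10 | 472 | 23 | 2.77 (1.68 to 4.58) | 0.00004 | 0.00006 |

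The first and last rows are the extremes. The 57/3 row is close to independence of the two signs within each APD column (306 × 166/894 = 56.8 and 23 × 10/80 = 2.9). Comparing 83/5 with 83/8 shows that three patients without APD can move the result across 0.05.

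Of the 167 × 11 = 1837 possible pairs, 640 give uncorrected p < 0.05 (576 with Yates, 618 with Fisher), all 640 with OR above 1. These are counts of tables, not probabilities.

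**The case against.** The strongest reply is that the document may mean two outcomes, one per sign. Each pair sums to 974, every figure carries its sign, and the Table 2 title names both signs as MN. On that reading the and/or is loose shorthand and the defect is one of wording. No reported result is shown to be wrong: no MN test or p value is printed, and chi-square is named only in general terms.

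The range of odds ratios also overstates the practical uncertainty. Each extreme requires complete overlap in one APD group and none in the other. Independence of the signs within APD groups gives OR 1.44, p = 0.125, in line with the two separate signs. With equal overlap fractions in both groups, p < 0.05 appears only at essentially zero overlap, and there Yates gives 0.062 and Fisher 0.061. Zero overlap is also unlikely if both signs come from the same motor process. Otherwise significance needs overlap to be more common without APD than with it. At y = 5, for example, x can be at most 57 (50% against 34%).

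Finally, complementary groups are the ordinary reading of a positive/negative pair, and nothing shows that one-sided signs were counted.

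Much of this stands. The sign counts are sound, and a non-significant composite is quite plausible. But the by-sign reading conflicts with a group list that has one MN pair and a definition that joins the signs, so that text would have to change. If the composite was meant, readable components do not supply it.

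**Conclusion.** The concern holds. MN as defined is not reported: its count, the overlap of the two signs and its table against APD are all absent, and two incompatible count pairs stand under its labels. This should be fixed, but it is confined to one part of a secondary outcome.

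The 33.8% to 51.8% range rests on two assumptions: counts limited to symmetric signs, and MN negative as the complement of MN positive. If one-sided signs were counted, the floor of 329 and the ceiling of 645 no longer hold. The table margins do not decide the significance of the MN-APD association either way. They do not show that it is significant, and they do not show that any record was misclassified.

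**What to change.** - Derive one MN variable per patient: positive if symmetric deformity or symmetric calluses are present, negative otherwise. Define the MN-negative group explicitly as the complement.
- Report its count, the number of patients with both signs, and its 2x2 table against APD with an odds ratio and 95% CI.
- Relabel the 329/645 and 176/798 figures, and the matching Table 2 rows, as components (calluses, foot deformity).
- State whether those counts are limited to symmetric signs.
- If two separate sign outcomes were intended, rewrite the Arm/Group Title and Description to say so.

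The cost is small: one derived variable, one added table and relabelling, from two signs already tabulated for all 974 records. If the counts include one-sided signs, recorded laterality must also be checked. The reported MN figure may change. Under the two-outcome option, only wording changes.
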